2.3 Additional Approaches to Primary Analyses

The primary treatment comparisons will be repeated in the following ways:

1. Include data only from subjects who complete the 36-month visit within the protocol window (34 to 38 months after randomization).
2. The primary analysis will be repeated, using only the initial assessments to identify failure at 3 years. If a change in refractive correction was necessary after formal failure criteria were met and confirmed by a retest, measurements reported for initial assessments performed with trial frames at the 37-month visit will replace measurements reported with trial frames at the 36-month visit if the assessment was failed.
3. The primary analysis will be repeated, imputing data for subjects with incomplete or no data at the primary outcome visit. Data will be imputed for subjects classified as “not failure” at 3 years who meet any of the following criteria: 1) the 36-month visit was not completed or was completed out of window, 2) a required 37-month visit was not completed, 3) an initial assessment or required retest was not performed and the available data indicates that the subject is a failure, or 4) no data was reported for an assessment, or an eye in the case of visual acuity. The imputation procedure is described in section 2.5.
4. The primary analysis will be repeated, adjusting for age at 36-month visit. Barnard’s Exact test does not allow for adjustment. Instead, binomial regression will be used to obtain the adjusted difference in failure rate between the treatment groups. If the model does not converge, Poisson regression using robust variance estimation will be used instead. If the Poisson model does not converge, logistic regression will be used to test the difference in treatment groups, controlling for age.
5. The distribution of the following baseline factors will be reviewed by treatment group: age, visual acuity, and stereoacuity. If factors appear to be confounders, defined as imbalance between treatment groups, binomial regression will be used to evaluate the treatment group difference in failure rates, controlling for all confounding factors. The characteristics will be categorized as follows:
 - a. Age: 1 to <2, 2 to <3, 3 to <4, 4 to <5, 5 to <6 years
 - b. Visual acuity: 20/20 or better, 20/25, 20/32, 20/40, 20/50
 - c. Stereoacuity: 40, 60, 100, 200, 400

If the primary analysis and additional approaches produce similar results, the primary analysis will be considered the definitive analysis and the additional approaches will be used to provide supportive evidence of the magnitude of treatment effect. However, if the results differ, exploratory analyses will be performed to evaluate the factors that have contributed to the differences.

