94 as failure must be confirmed, subjects who complete the 36-month visit will not be
95 considered to have met failure criteria for a condition if a required test or retest was not
96 performed.
- 97 4. Data will be considered missing if not completed within the analysis window. The 36-
98 month assessment must be completed no earlier than 33 months (1005 days) and no later
99 than 42 months (1282 days). Subjects will be excluded from analysis if the 36-month
100 visit is not completed within the analysis window.
- 101 5. The 37-month visit is an extension of the 36-month visit. No analysis window is defined
102 for the 37-month visit. If required and collected, data at the 37-month visit will be used in
103 analysis. Subjects will be included in analysis if the 36-month visit was completed within
104 the analysis window. See Table 1 and Figure 1 below for clarification.
- 105 6. Imbalances between groups in important covariates measured at baseline are not expected
106 to be of sufficient magnitude to produce confounding. However, as a complement to the
107 primary analysis, the presence of confounding will be evaluated by including in the
108 model factors that appear to be imbalanced between treatment groups and are associated
109 with visual acuity, stereoacuity, or strabismus.

110
111 Barnard’s exact test does not allow for the adjustment of covariates. Binomial regression was
112 used to compare treatment groups when the model was adjusted for possible confounders.

Table 1: Analysis of Data based on Visit Completion

36-Month Visit			37-Month Visit Required	37-Month Visit Completed	Primary and Secondary Analyses ^a	Additional Approaches to Primary Analysis (Imputation) ^b
In Window	Out of Window	Not Completed				
-	-	X	-	-	Excluded	Impute
X			No	-	Data included	Data included
X			Yes	Yes	Data included	Data included
X			Yes	No	Data included	Impute
	X		No	-	Excluded	Impute
	X		Yes	Yes	Excluded	Impute
	X		Yes	No	Excluded	Impute

X indicates when visit was completed

-Visits are considered completed if data was collected at the visit. Completion status is not dependent on the amount of data collected at the visit.

[figure not shown]
^aSubjects will be included in the primary and secondary analyses as long as the 36-month visit was completed. Seeing as failure must be confirmed, subjects who complete the 36-month visit will not be considered to have met failure criteria for a condition if a required test or retest was not performed.

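### Beyond the fixed adjustment for age at 36 months, covariates for the supportive adjusted failure-rate comparison are picked by observed imbalance, under two rules that can disagree and have no threshold

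*SAP*

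**What the plan says.** The primary comparison in SAP section 2.0 is an unadjusted Barnard's exact test at two-sided 0.05, done separately in two age cohorts. Three provisions then deal with covariate adjustment of the failure rate.

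- **Section 2.2, principle 6.** The plan starts from the view that "Imbalances between groups in important covariates measured at baseline are not expected" to be large enough to confound. It will still check, using "factors that appear to be imbalanced between treatment groups and are associated" with acuity, stereoacuity or strabismus. It gives no list of factors.
- **Section 2.3, item 4.** "The primary analysis will be repeated, adjusting for age at 36-month visit". This is unconditional, and it has a fallback from binomial regression to Poisson with robust variance and then to logistic regression.
- **Section 2.3, item 5.** "The distribution of the following baseline factors will be reviewed by treatment group: age, visual acuity, and stereoacuity". The rule follows: "If factors appear to be confounders, defined as imbalance between treatment groups", then "binomial regression will be used to evaluate the treatment group difference in failure rates, controlling for all confounding factors". Categories are given for the three factors. There is no cut-off for imbalance, and no fallback is attached to this item.

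The closing paragraph of section 2.3 treats the primary analysis as definitive if the additional approaches agree with it. If they do not, it calls for exploratory work.

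**The concern.** In a randomised trial a baseline imbalance arises by chance. What makes a covariate worth adjusting for is its relation to the outcome. An imbalanced factor unrelated to failure adds a term and removes no bias. A strong predictor with a small imbalance can shift the estimate and yet pass the screen unnoticed. Defining a confounder by imbalance alone therefore uses the wrong criterion, and the plan contradicts itself by requiring association in one place and not in the other.

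What is at stake is a supportive analysis that feeds the agreement check in section 2.3. If judgement decides whether it exists and what it contains, its agreement or disagreement with the primary result is hard to interpret. The trial also gives up whatever precision fixed prognostic covariates would bring.

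**Working it through.** The SAP states no figure on this point, so there is none to reproduce.

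**1. The two rules side by side**

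| | 2.2, principle 6 | 2.3, item 5 |
|---|---|---|
| Candidate pool | open | age, acuity, stereoacuity |
| Imbalance needed | yes, by appearance | yes, by appearance |
| Association needed | yes | no |
| Threshold | none | none |

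Two cases separate them. An imbalanced factor among the three that is unrelated to outcome enters under item 5 only. An imbalanced prognostic factor outside the three can enter under principle 6 only. Baseline spherical equivalent and anisometropia are such factors: section 3.7 uses both as baseline subgroups, so they are collected, but they are not in item 5.

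**2. Comparison with the SAP's other models.** Section 3.2 adjusts acuity for age at the 36-month exam and enrolment acuity. Section 3.5 adjusts stereoacuity for age and anisometropia (from the most recent refraction). Both do so whatever the balance. For the failure rate, only age at 36 months is fixed in this way.

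**3. How far an unstated threshold matters (illustration).** Inputs: three candidate factors (item 5), two cohorts (section 2.0). Assumptions not in the SAP: factors are independent, and imbalance is judged at an effective level a.

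P(at least one of three looks imbalanced) = 1 − (1 − a)^3; for both cohorts together, 1 − (1 − a)^6.

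| a | per cohort | either cohort |
|---|---|---|
| 0.05 | 1 − 0.95^3 = 14.3% | 1 − 0.95^6 = 26.5% |
| 0.10 | 1 − 0.90^3 = 27.1% | 1 − 0.90^6 = 46.9% |
| 0.20 | 1 − 0.80^3 = 48.8% | 1 − 0.80^6 = 73.8% |

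**4. Effect on error rate (illustration).** A normal-theory simulation with 400,000 replicates used one covariate with assumed correlation r of 0.2 to 0.5 with outcome. The imbalance statistic z_x and the adjusted test statistic e are independent standard normals, and the unadjusted statistic is r·z_x + √(1 − r²)·e. The screen fires at the same three assumed cut-offs. Type I error at nominal two-sided 0.05:

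- always adjust: 0.050 for every r;
- adjust only if imbalanced: 0.037 to 0.049, which is conservative;
- take the more favourable of adjusted and unadjusted: 0.059 to 0.074.

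The SAP does not provide for the last of these.

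**5. Model size.** In the older cohort, item 5's categories entered as unordered factors would use up to 2 (age) + 4 (acuity) + 4 (stereoacuity) = 10 degrees of freedom. Five continuous terms would use 5.

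**The case against.** Principle 6 can be read as the general statement and item 5 as its working version. Baseline acuity and stereoacuity correspond to two of the outcomes that principle 6 names, and age bears on the age-norm failure criteria, so association may be implied by the choice of list. This has some force, and it is why the rules can differ rather than must differ. But item 5 writes its own definition and leaves association out, and the missing threshold remains.

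A reader might infer more than the document supports:

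- **That the primary result's type I error is at risk.** The Barnard test takes no covariates, and section 2.3 does not let a more favourable adjusted result replace it. The simulated inflation needs a choice that the plan does not offer.
- **That no adjusted analysis exists unless imbalance is seen.** Item 4 always fits one.
- **That refractive error and anisometropia are excluded altogether.** Principle 6 is open and could admit them, and section 3.7 tabulates failure by both. The omission is item 5's.
- **That covariates are chosen by looking at outcomes.** Item 5 screens baseline distributions only, and the SAP does not say when the balance review takes place. The version history does show that the SAP was first written after study completion and that version 3.0 followed review of results in the manuscript. That leaves less protection for a rule based on appearance, but it does not show misuse.

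It is also fair that the SAP does not establish which factors are prognostic and gives no sample size or event count. The gain in precision cannot be quantified.

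**Conclusion.** The point holds for a supportive analysis. Two provisions define the covariates for the extra adjusted model differently, neither has a threshold, and item 5's criterion of imbalance alone is not a sound basis for adjustment. Whether that model is run, and with which terms, depends on chance imbalance and judgement.

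The 14%, 27% and 49% per cohort are illustrative. They rest on assumed cut-offs and on independence, and correlation among age, acuity and stereoacuity would lower them. No inflation of error is shown for the plan as written, and the conservative 0.037 to 0.049 rests on assumed correlations. A correction is worth making because the two definitions need reconciling in any case, and a fixed set costs little more than choosing between them.

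**What to change.** Replace the imbalance screens in section 2.2, principle 6, and section 2.3, item 5, with one supportive adjusted analysis per cohort, run whatever the observed balance.

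- **Covariates.** Name a fixed set chosen on prognostic grounds. An example is baseline age, spherical equivalent and anisometropia as continuous terms, plus baseline acuity and stereoacuity in the cohort where they are measurable.
- **Missing baseline values.** State how children without baseline acuity or stereoacuity are handled.
- **Convergence.** Apply item 4's sequence of binomial, robust Poisson and logistic regression to this model too.
- **Status.** Keep it supportive, and label it post hoc if it is set after outcome data were reviewed.

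The cost is a change of SAP wording. Refractive error and anisometropia are already collected, and the other factors are those that item 5 itself reviews. The downside is a few more model terms and some risk of non-convergence, which the fallback addresses.

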2.4 Multiple Imputation

Multiple imputation using logistic regression will be used to impute 36-month failure status and will be performed separately for each primary cohort. Imputation in each cohort will be based on the presence of deterioration prior to 3 years and will be stratified by treatment group. The proportion of subjects who failed at 3 years will be tabulated for each imputed data set, and the results will be combined using the MiAnalyze procedure in SAS 9.4 to generate valid statistical inferences.

It is recognized that differential loss to follow up or a difference in the distribution of loss to follow-up times may introduce bias to the multiple imputation model. Prescribing or withholding treatment may influence a parent’s decision to keep their child enrolled in the study, therefore results may be subject to bias if subjects receiving one treatment regimen are more likely to withdraw from the study. Results may also be subject to bias if subjects in one treatment group tend to remain in the study longer than subjects in the other. Deterioration is identified during the

follow-up period, so the chance of meeting deterioration criteria increases with the number of completed visits.

The protocol states that the last-observation-carried-forward method would be used in addition to multiple imputation, but this is not possible as failure is only assessed at the 36-month visit.

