24 criteria (below) at 36 months post-randomization. The primary analysis will be performed
25 separately for each of the two primary cohorts.

26
27 The null hypothesis of no difference between the treatment groups will be rejected if the
28 proportion meeting failure criteria in immediate glasses is significantly lower or higher than the
29 proportion in observation, based on the Barnard's exact test with 2-sided type I error of
30 $\alpha=0.05$.

31
32 Although Fisher's exact test was initially proposed, this was changed to Barnard's exact test to
33 allow for the calculation of a confidence interval on the difference between proportions, which is
34 consistent with the p-value from the test.

35
36
37 **2.1 Primary outcome**

38 At the 36-month outcome visit, each subject's condition will be classified as either failure or not
39 failure as follows:

40
41 Failure = ANY of the following criteria are met at the masked 36-month visit both with and
42 without correction in trial frames (without prism or bifocal):

- 43
- 44 1. Any measurable heterotropia in primary gaze in the distance (3 meters) or at near (1/3
45 meter) not correctable with distance refractive correction alone
 - 46 2. Strabismus surgery prior to the 36-month outcome exam
 - 47 3. Visual acuity below age norms in either eye
48 a. To be below age-normal, visual acuity in the eye must fall below age-normal
49 values on both test and retest, both with and without correction.
50 b. Visual acuity will be obtained for each eye.
 - 51 4. ≥ 2 logMAR lines of IOD if visual acuity is 20/25 or worse in the better eye (applies to
52 IOD either with or without correction but not one eye with and one eye without)
 - 53 5. ≥ 3 logMAR lines of IOD if visual acuity is 20/20 or better in the better eye (applies to
54 IOD either with or without correction, but not one eye with and one eye without)
 - 55 6. Stereoacuity at near by Randot Preschool test below age normal values

56
57 Not Failure = NONE of the criteria for failure are met

58
59 If a subject meets any failure criteria (with the exception of strabismus surgery prior to the 36-
60 month outcome exam), the visual condition that is considered to be failed must be retested by the
61 masked examiner (*section 3.6.1*) using the same procedures outlined in *section 3.6.1* of the
62 protocol. The subject must be given a 10-minute break prior to retesting each failed criterion.

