63 Failure criterion must be confirmed by a retest both with and without correction to be considered
64 a failure.

66 If failure is confirmed and the subject requires a change in glasses (*section 4.3* of the protocol),
67 the 36-month outcome exam is repeated on a different day 4 weeks \pm 1 week later (subsequently
68 referred to as the 37-month visit) by the masked examiner with the child wearing their new
69 glasses. Testing without correction does NOT need to be repeated. Failure will be assessed at this
70 post-36 month exam, and the subject will be classified as a failure if he/she meets any of the
71 failure criteria above. If the subject meets any failure criteria (with the exception of strabismus
72 surgery), the visual condition that is considered to be failed must be retested by the masked
73 examiner using the same procedures outlined above. Failure must be confirmed without
74 correction at the 36-month exam and with correction at this repeat outcome exam 4 weeks later to
75 be considered a failure.

77 **2.2 Principles to be Followed in Primary Analysis**

78 The following principles apply to the primary treatment comparison:

- 79 1. The primary treatment comparisons will be performed using a modified “intent-to-treat”
80 analysis principle. The data of all randomized subjects completing the 36-month exam
81 will be included in the analysis regardless of whether the assigned treatment was actually
82 received. Data from subjects who receive alternate treatment (i.e. glasses for subjects
83 assigned to observation who did not meet deterioration criteria and vice versa) will be
84 analyzed according to randomization group. There will be no imputation of data for
85 subjects who are lost to follow-up or withdrawn from study prior to the primary outcome,
86 defined as the failure status at the 36-month visit if the 37-month visit is not required and
87 failure status at the 37-month visit if required.
- 88 2. Subjects who meet failure criteria at the 36-month assessment and have significant
89 changes in their cycloplegic refraction are prescribed glasses and required to return
90 within 4 weeks to be retested in their updated correction. If this happens, the results of the
91 36-month examination without correction and the 37-month examination with correction
92 will be used to determine failure status in the primary analysis.
- 93 3. Subjects will be included in analysis as long as the 36-month visit was completed. Seeing

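### The imputation analysis ignores the failing 36-month result of attendees who lack only a confirming retest or 37-month visit, and does not say how deterioration is coded for children lost early

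*SAP*

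**What the plan says.** In the primary analysis an attendee whose required test or retest is missing is not counted as a failure on that condition (section 2.2, principle 3, and Table 1 note a). Table 1 keeps a child who missed a required 37-month visit in the primary analysis under the same rule.

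Approach 3 in section 2.3 then imputes children classified as not failure under four criteria. The first is an absent or out-of-window 36-month visit. The other three concern attendees: "a required 37-month visit was not completed"; "an initial assessment or required retest was not performed and the available data indicates that the subject is a failure"; and "no data was reported for an assessment, or an eye in the case of visual acuity".

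The text adds "The imputation procedure is described in section 2.5", but the SAP has no such section; the procedure is in section 2.4. There, a logistic model for overall failure status is run per cohort, and "Imputation in each cohort will be based on the presence of deterioration prior to 3 years and will be stratified by treatment group". No 36-month measurement, length of follow-up or baseline factor is named as a predictor.

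Section 2.4 recognises that loss, or its timing, differing between arms may bias the model, and that deterioration is more likely to be recorded the more visits are completed. The model is not changed in response.

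**The concern.** Two of the attendee groups are chosen because their observed data suggest failure. A 37-month visit is required only after failure has been confirmed at 36 months and the glasses need changing (section 2.1). The other group has a failing result with a test or retest missing. The model discards the observation that selected them: such a child and a never-examined child with the same cohort, arm and deterioration status receive the same failure probability. The SAP does not mention this.

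It matters because the closing paragraph of section 2.3 makes the primary analysis definitive when the additional approaches agree with it. Approach 3 ought to test the rule that counts these attendees as not failures. If it restores only part of the failures so missed, agreement is weak reassurance.

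The secondary issue concerns absent children. A child lost at month 6 without deterioration has not been seen to remain free of it to month 36. Section 3.1 handles the same event by Kaplan-Meier, which censors such a child. Section 2.4 has no counterpart.

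**Working it through.** The SAP gives no failure, deterioration, retest or loss rate, so there is no planned figure to reproduce. **Every rate below is an assumption.**

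**1. Attendees with a failing result**

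Let s be the share of an arm with such a result and no confirmation, c the probability that it would be confirmed, and d the probability the model draws. The arm's failure rate is then too low by s × (c − d). The primary analysis corresponds to d = 0.

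Take s = 0.05, and d between 0.15 (not deteriorated) and 0.50 (deteriorated).

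| Case | c | Primary (d = 0) | d = 0.15 | d = 0.50 |
|---|---|---|---|---|
| Missing retest | 0.50 | 2.5 points | 1.75 | 0 |
| Missing retest | 0.70 | 3.5 | 2.75 | 1.0 |
| Missing retest | 0.90 | 4.5 | 3.75 | 2.0 |
| Missed 37-month visit, if few failures persist | 0.30 | 1.5 | 0.75 | −1.0 |

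At c = 0.70 the imputation restores 0.05 × 0.15 = 0.75 to 0.05 × 0.50 = 2.5 of the 3.5 points missed.

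Why d is probably below c for retests: with one condition, let i be the probability of failing the initial test and m the share of initial failures with no retest, missing at random. Ignoring deterioration, the model draws at i(1 − m)c / (1 − im), so the understatement factor is (1 − im) / [i(1 − m)].
- i = 0.5, m = 0.1: 0.95 / 0.45 = 2.1.
- i = 0.2, m = 0.2: 0.96 / 0.16 = 6.0.

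This is not a certainty. Overall failure can arise from any of several conditions, so d could exceed c for a condition that is seldom confirmed.

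For a missed 37-month visit, section 2.1 requires failure to be confirmed without "correction at the 36-month exam and with correction at this repeat outcome exam 4 weeks later to" count. The 37-month test is done in new glasses, so c may be low and the error can take either sign, as the last row shows.

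**2. Children lost early without deterioration, if coded as 'no deterioration'**

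Let F be 36-month deterioration, spread evenly over six intervals: h = 1 − (1 − F)^(1/6). Let loss be equally likely after k = 0, …, 5 intervals and unrelated to outcome. A lost child is undeteriorated at loss but would deteriorate later with probability (1 − h)^k × [1 − (1 − h)^(6−k)]. Averaging over k and multiplying by the gap in failure probability between deteriorated and undeteriorated children gives the shortfall per lost child.

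- F = 0.40 (observation), gap 0.50 − 0.15 = 0.35: 0.0759.
- F = 0.10 (glasses), same gap: 0.0201.
- With 15% loss in each arm: 0.15 × 0.0759 = 0.0114 and 0.15 × 0.0201 = 0.0030. The difference is 0.8 points too small, against a true 0.30 × 0.35 = 10.5 points.
- Weaker link (0.30 against 0.20, gap 0.10): 0.2 points too small, against a true 3.0.
- Extreme case, all loss at month 0, gap 0.35: 0.15 × 0.30 × 0.35 = 1.6 points.
- Gap of zero: no bias.

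The bias in the difference changes sign only if glasses loss exceeds 0.0759 / 0.0201 = 3.8 times observation loss.

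**The case against.** - **Approach 2 already uses the failing data.** It classifies children "using only the initial assessments to identify failure at 3 years", so it covers part of both groups. That stands. But it drops the confirmation rule for every child, which changes the outcome, and it does not bring in absent children.
- **Table 1 note b protects failing children.** A reader might infer this, since it exempts from imputation those who met failure criteria despite incomplete testing. Read with note a, a condition lacking its retest has not been met, and section 2.3 item 3 lists these children for imputation. Note b therefore covers children already failing on another condition.
- **The timing bias is disclosed.** Largely so, but only for loss or timing that differs between arms. Part 2 shows a bias under equal loss, because section 3.1 expects more deterioration under observation. It is small.
- **The link between deterioration and failure is assumed.** This stands. Children assigned to observation are prescribed glasses once they deteriorate (section 1.0), which could weaken the link.
- **Missing retests may be few.** This stands. The retest follows a 10-minute break, and the SAP gives no counts. The 5% share only sets a scale.
- **A new model this late adds flexibility.** This stands, and limits how much should be changed. By the version history, the SAP was first written after study completion and revised during final manuscript review.

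**Conclusion.** The point holds as a limited fault in one supportive analysis. As written, section 2.4 discards the observed failing result of attendees whom section 2.3 selects because of it. For missing retests the imputed failure is probably too low: 0 to 3.75 points of an arm's rate, if 5% of the arm is affected and 50% to 90% would be confirmed. For missed 37-month visits the draw is uninformed and its direction unknown. Approach 3 is thus a weak check of the not-failure rule, partly backed by approach 2.

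The secondary point is conditional on the coding and on deterioration predicting failure. It is worth about 0.2 to 0.8 points of the difference at 15% evenly spread loss in each arm, and zero without that link.

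Four stronger readings are not supported:
- That the SAP codes early dropouts as non-deteriorators. No coding rule is stated; this is inferred from the predictor and the SAP's own caveat.
- That imputed failure is too low for every attendee. The 37-month group shows why not, and no direction is claimed for a missing assessment or eye.
- That the treatment effect could reverse. Only the sign of a small bias can change; the direction between arms of the first error is not determined.
- That the primary result is affected. It uses no imputation.

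**What to change.** In the imputation analysis:

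1. **Missing retest:** impute confirmation from children who failed the same initial test and were retested.
2. **Missed 37-month visit:** impute that result from children with confirmed 36-month failure who attended it.
3. **Few donors in either case:** pool the arms, with arm as a covariate.
4. **Absent children:** do not treat deterioration as known to be absent after the last completed visit; for example, impute later deterioration first and failure second. State the coding rule.
5. **Reporting:** label this a revised sensitivity analysis, show it beside the original model, and tabulate by arm how many children fall under each of the four imputation criteria.
6. **Cross-reference:** in section 2.3 item 3, point to section 2.4.

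The cost is SAP wording plus reprogramming and rerunning one analysis on existing data. The drawbacks are small donor groups and late specification, hence the label. A full component-by-component rebuild is not needed. If even this is judged too much, the minimum is to keep the model, state both limitations, give the counts and correct the reference.
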